### Partial or Missing Dates:

The following conventions will be used to impute missing portions of dates for adverse events and concomitant medications. Note that the imputed values outlined here may not always provide the most conservative date. In those circumstances, the imputed value may be replaced by a date that will lead to a more conservative analysis.

#### A. Start Dates

- 1) If the year is unknown, then the date will not be imputed and will be assigned a missing value.
- 2) If the month is unknown, then:

- i) If the year matches the first dose date year, then impute the month and day of the first dose date.
  - ii) Otherwise, assign 'January.'
- 3) If the day is unknown, then:
  - i) If the month and year match the first dose date month and year, then impute the day of the first dose date.
  - ii) Otherwise, assign the first day of the month.

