A blinded independent rater who will not be present during any of the therapy sessions will administer the CAPS and assess the participant on the GAF. To establish independent rater reliability, the investigators will have the option to video record the screening CAPS interview in as many instances as necessary. The C-SSRS will also be

administered at screening to assess suicide risk. Suicide risk will also be assessed via psychiatric interview. The Clinical investigator and independent rater will use medical records, communication with the participant's treating psychiatrist or therapist if applicable and psychiatric interview to assess potential risk to others. The participant will complete the BDI-II, PTGI (in reference to time since the trauma), PSQI, DES-II and NEO-PI. The entire visit should take between 1.5 and 2.5 hours. Screening may take place over more than one day and up to four months prior to Visit 1 (enrollment). The participant may also have the first preparatory session (Visit 2) prior to enrollment.

If eligibility is confirmed, the participant will be enrolled and will be issued a subject number and contacted to schedule introductory non-drug psychotherapy sessions and first experimental session. Any participant who must discontinue a medication will, after consultation with the prescribing physician, be given a schedule to begin tapering off that medication so washout will be completed before the first experimental session, with the interval between the start of washout (the last day the medication was taken) and the first experimental session being at least five times the drug and active metabolites' half-life, plus one week for stabilization. The first experimental session will be scheduled to occur after washout is complete, if applicable.

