# 9.0 Collection of Concomitant Medications and Tapering Instructions

All medications, over the counter (OTC) and prescription will be collected from screening through 7 days after the final experimental session. From 7 days after the final experimental session through study termination only medications taken to treat SAEs and psychiatric AEs will be collected.

Concomitant medications will be recorded during screening. Any psychoactive drugs will be tapered in an appropriate fashion to avoid withdrawal effects. They will be discontinued long enough before the experimental session to avoid the possibility of drug interactions (the interval will be at least 5 times the half-life of the particular drug or its active metabolites, plus one week for stabilization). If necessary, the investigators will make plans for tapering off and discontinuing any contraindicated medication upon enrollment, in consultation with the prescribing physician.

The investigators will request information about any changes in medication. Medications taken during the course of the protocol, including medications taken to treat AEs, will be recorded on a concomitant medications CRF. Participants must be willing to refrain from taking any psychiatric medications until after the end of Stage 1 or Stage 2, with the exception of gabapentin when prescribed for pain control or stimulants for ADHD taken at baseline provided that they are discontinued 5 half lives before each MDMA session and are not restarted until 10 days after each MDMA administration. The investigators may prescribe a designated rescue medication in the event of symptoms that require it during or after the experimental session (e.g. insomnia or severe anxiety that does not respond to other management outlined in the treatment manual).

Subjects must be willing to refrain from taking any psychiatric medications during Stage 1 and Stage 2, with the exception of gabapentin when prescribed for pain control. If the subject is on stimulants for ADHD at baseline, they can continue to use them at the same dose and frequency as long as they discontinue five half-lives before each experimental session and do not restart for 10 days after each experimental session.

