#### B. Stop Dates

- 1) If the year is unknown, then the date will not be imputed and will be assigned a missing value.
- 2) If the month is unknown, then assign 'December.'
- 3) If the day is unknown, then assign the last day of the month.

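### SAP 8.2 imputes some partial start dates to the first dose date without looking at the stop date, so a record that ended before dosing can be given a start after its own end

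*SAP*

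**What the plan says.** The date conventions stand in SAP 8.2 under Partial or Missing Dates. Their scope is stated as: "The following conventions will be used to impute missing portions of dates for adverse events and concomitant medications".

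- **Start, month missing (A.2(i)):** "If the year matches the first dose date year, then impute the month and day of the first dose date". In any other year the start goes to January.
- **Start, day missing (A.3(i)):** "If the month and year match the first dose date month and year, then impute the day of the first dose date". In any other month the start goes to the first of the month.
- **Stop, day missing (B.3):** "If the day is unknown, then assign the last day of the month". With the month missing, B.2 assigns December.

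The one safeguard follows an acknowledgement that the imputed date may not be the most conservative: "In those circumstances, the imputed value may be replaced by a date that will lead to a more conservative analysis".

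The protocol makes records that end before the first dose an ordinary part of the data. Section 6.2.1 schedules tapering so that "washout will be completed before the first experimental session", and Section 9.0 adds that "the interval will be at least 5 times the half-life of the particular drug or its active metabolites, plus one week for stabilization". On recording, Section 9.0 says: "All medications, over the counter (OTC) and prescription will be collected from screening through 7 days after the final experimental session". Section 8.3 and the Stage 1 Time and Events table collect serious events, psychiatric-status events and events leading to withdrawal from Visit 1. The first dose is at Visit 5.

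**The concern.** A.2(i) and A.3(i) suit a record that is ongoing or has no end date: if the start might be on or after dosing, they date it to dosing. They do not suit a record already known to have ended before dosing, yet nothing in the start or stop rules separates the two cases or requires the start to be no later than the stop.

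Two planned outputs depend on these dates.

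- **Adverse events.** SAP 8.9.4 makes adverse event reporting the primary safety measure and treats events arising after dosing as treatment-emergent. Protocol 7.3 notes that stopping PTSD medication can shift mood and may raise the likelihood of suicidal ideation, so a psychiatric event during washout is foreseeable. If it resolved before Visit 5 and its onset is only partly dated, the rules place its onset on the MDMA dosing day.
- **Medications.** SAP 8.8 summarizes use before and after informed consent. A drug started before consent and then tapered could have its start moved to the dosing day, which is after consent, and so be lost from the before-consent side.

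**Working it through.** The SAP gives no figure to reproduce, so the check applies the rules literally.

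**General argument.** Let F be the first dose date and S the stop date, with S < F. Where A.2(i) or A.3(i) applies, the imputed start equals F. Hence start = F > S for every such record.

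**Worked records.** The calendar dates are illustrative assumptions, with F = 20 June 2013.

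| Record | Imputed start | Stop used | Start minus stop |
|---|---|---|---|
| Drug, start 2013 (month unknown), stop 1 May 2013 | 20 June | 1 May | 50 days |
| Same drug, stop May 2013 (day unknown) | 20 June | 31 May by B.3 | 20 days |
| Drug, start June 2013 (day unknown), stop 10 June | 20 June | 10 June | 10 days |
| Psychiatric event, start June 2013 (day unknown), resolved 12 June | 20 June | 12 June | 8 days |
| Drug, start 2012 (month unknown), stop 1 May 2013 | 1 January 2012 | 1 May 2013 | no conflict |
| Drug, start 2013, stop 2013 (both months unknown) | 20 June | 31 December by B.2 | no conflict |

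**Enumeration.** Take every true pair with start ≤ stop < F. If k days precede F in the relevant period, there are k(k+1)/2 pairs.

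| Assumed F | Month missing, start in dose year | Day missing, start in dose month |
|---|---|---|
| 15 March 2013 | k = 73: 2,701 of 2,701 wrong | k = 14: 105 of 105 wrong |
| 20 June 2013 | k = 170: 14,535 of 14,535 wrong | k = 19: 190 of 190 wrong |
| 28 November 2013 | k = 331: 54,946 of 54,946 wrong | k = 27: 378 of 378 wrong |

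**Size of the error for tapered drugs.** By Protocol 9.0 the stop must precede the session by at least 5 half-lives plus 7 days, and the imputed start is F. With half-lives from the Medication Tapering Table, the imputed start is later than the true stop by at least:

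- zolpidem: 5 × 2.5 h = 12.5 h ≈ 0.5 days; 0.5 + 7 = 7.5 days
- sertraline: 5 × 26 h = 130 h ≈ 5.4 days; 5.4 + 7 = 12.4 days
- fluoxetine, upper half-life of 9 days: 45 + 7 = 52 days

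With minimum gaps of 8, 13 and 52 days imposed, the month-missing share stays at 100%. The day-missing share is also 100% at 8 and 13 days. At 52 days no day-missing record can arise, because start and stop cannot both fall in the dose month.

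**After the change.** The start becomes 1 January, or the first of the known month. The true start is no earlier than that and no later than S, so the imputed start cannot exceed S. Rerunning the enumeration gives 0 start-after-stop records in every scenario. The first worked record moves from 20 June to 1 January 2013.

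**The case against.** **The override clause.** The SAP calls its imputed values replaceable, so they are defaults and a programmer could correct an impossible interval. That is true, but the clause is optional, does not define conservative, and says nothing about date order. For an adverse event, conservative is usually read as keeping it treatment-emergent, which would preserve the error.

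**Few records qualify.** Before Visit 5 only three event categories are collected. The Time and Events table puts Visit 5 at most 7 weeks after Visit 1, with preparatory visits between, and serious events are reported within 24 hours or by the next working day. An unknown month is therefore unlikely for an event; an unknown day in the dose month is the narrow remaining case. Drugs started in an earlier year are unaffected. An event with a recorded pre-dose resolution also plainly did not occur after dosing, so a careful analyst would not count it. All of this stands and limits the consequence. It does not make the rule correct.

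**Stronger readings that a reader might infer.**

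- *The rules show tapered drugs as taken during MDMA sessions.* The start rules do not. They give an impossible interval, which a date-order check would reveal.
- *False records of excluded treatment lead to protocol deviations.* SAP 8.3 lists that category but does not say deviations are derived from imputed dates, and its definition of a major deviation does not mention it.
- *The month-end stop rule often carries a tapered drug past session 1.* Any such frequency must assume that the last-dose day is unknown. Protocol 6.2.1 counts the washout from that day, so the site needs it to schedule session 1. SAP 8.8 also splits at consent rather than first dose, and tapering follows consent, so a later imputed stop leaves the drug on the same side.

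**Conclusion.** The point holds as a logic defect in A.2(i) and A.3(i). Every record to which either rule applies, and whose stop is known to precede the first dose, receives a start after its stop. This includes a stop known only to an earlier month than the dose.

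The share is 100% of qualifying records and follows from the wording alone; the calendar dates used above only illustrate it. The number of qualifying records is not in the documents and is probably small. In the low or medium dose arm one misclassified subject would be 1/6, or 17%, of the arm. That is a sense of scale, not an estimated risk. Misclassification also assumes that treatment-emergent status and the consent split are programmed from imputed dates without a further check, on which the SAP is silent.

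The primary CAPS-4 comparison does not use these dates. The documents do not support extending the point to apparent drug use across sessions, to protocol deviations, or to a stated error rate for the stop rules. The correction is worth making because it is nearly free and bears on the safety and medication tables.

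**What to change.** Add to SAP 8.2:

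1. Apply A.2(i) and A.3(i) only if the stop date is missing, or is on or after the first dose date.
2. Otherwise impute the earliest start compatible with the known parts: 1 January if the month is missing, the first of the month if only the day is missing. Require every imputed start to be no later than the stop.
3. Class a record as pre-dose whenever the known parts of its stop date place it before the first dose.

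Do not add a cap that sets a washout drug's imputed stop to the day before the first dose. That date lies inside the interval required by Protocol 9.0, so it would itself suggest an incomplete washout. It also presumes that the drug was stopped before dosing and could hide a genuinely late stop.

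The cost is a few sentences in the SAP and a few lines of code, with no change to data collection, sample size or the efficacy analyses.

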#### B. Stop Dates

- 1) If the year is unknown, then the date will not be imputed and will be assigned a missing value.
- 2) If the month is unknown, then assign 'December.'
- 3) If the day is unknown, then assign the last day of the month.

### 8.4 Pooling of Investigator Centers

All subjects in this study come from one investigational center.

### 8.5 Baseline Values

Baseline values are from screening/baseline visit for all measures, except C-SSRS. For C-SSRS, pre-enrollment scores will be used as a measure of ‘lifetime’ suicidal ideation and behavior, and preparatory session 2 (visit 3) pre-drug Since Last Visit C-SSRS scores will be used as ‘baseline.’ If a subject was not administered the C-SSRS at preparatory session 2 (visit 3), then ‘baseline’ scores will be from preparatory session 3 (visit 4).

## **8.6 Subject Disposition and Dosing Summary**

All subjects enrolled in the study (i.e., who sign informed consent and complete inclusion/exclusion criteria) will be included in the summary of subject disposition and accountability. No inferential statistical tests will be performed. The tabulation of number of subjects in each treatment group and overall will be displayed for all subjects who are randomized and had any treatment exposure, in the Safety Population, in the ITT Population, and in the PP Population. The number and percent of subjects who completed or discontinued the study will be displayed for each treatment group and overall together with reasons for early termination, where the percent is with respect to the total number of randomized subjects in that treatment group. The timepoint of doses and total MDMA (mg) administered will be summarized by treatment group for the Safety, ITT and PP Populations.

## **8.7 Demographics and Baseline Characteristics**

Subject demographic data and baseline characteristics will be summarized descriptively by treatment group and overall. The demographic data and baseline characteristics will be summarized for the ITT and Crossover Populations.

## **8.8 Prior and Concomitant Medications**

The number and percent of subjects who took medications prior to and after signing informed consent will be summarized descriptively for each treatment group. Concomitant medications will be summarized similarly. Prior and concomitant medications will be summarized for the Safety Population.

## **8.9 Efficacy Analyses**

For all primary, secondary and exploratory endpoints descriptive statistics (n, mean, standard deviation, median, range, or counts and percentages where appropriate) will be provided by treatment group.

### **8.9.1 Primary Efficacy Analyses**

Clinician Administered PTSD Scale-4 (CAPS-4)

The primary efficacy evaluation is the change from baseline to the primary outcome timepoint (visit 13) in the CAPS-4 Global Severity score of PTSD (difference score). The primary efficacy comparison will be made with ANOVA at an alpha level of 0.05. If the null hypothesis rejects, pairwise comparisons among the treatment groups will be made with t-tests. If the parametric assumptions for the ANOVA analyses are not met, the analogous nonparametric methods will be used (Kruskall-Wallis, Wilcoxon Rank-Sum).

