# 3.1 Primary Objective

 Assess changes in PTSD symptoms via Clinician-Administered PTSD Scale (CAPS) global scores in participants receiving by condition in the randomized study arms at baseline and the primary endpoint, one month after the second experimental session.

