#### 5.3.1 Inclusion Criteria

Individuals eligible to be enrolled into this protocol are participants who:

- 1. Meet DSM IV criteria for current PTSD with a duration of 6 months or longer resulting from traumatic experience during military service;
- 2. Have a CAPS score of 50 or higher, indicating moderate to severe PTSD symptoms;
- 3. Have had at least one unsuccessful attempt at treatment for PTSD with medication, such as an SSRI, SNRI, or mirtazapine, or one unsuccessful treatment with any form of psychotherapy for which there exists a controlled trial indicating efficacy in the treatment of PTSD. This includes cognitive-behavioral therapy

(including exposure therapy), stress inoculation training, including anxiety management, insight-oriented psychotherapy, and EMDR.

OR who discontinued treatment due to either:

- Inability to tolerate psychotherapy for PTSD (e.g. persistent "overengagement" when attempting Prolonged Exposure Therapy) or
- Inability to tolerate psychopharmacology for PTSD due to treatment-emergent side effects;

Treatment will be deemed to have been unsuccessful if the participant continues to meet criteria for current PTSD following the treatment.

- 4. Are at least 18 years old;
- 5. If in ongoing psychotherapy at the time subjects are recruited into the study, participants may continue to see their outside therapist during the course of the study. Participants must sign a release for the investigators to communicate directly with their therapist. Subjects may not change therapists, increase the frequency of therapy or commence any new type of therapy until after the evaluation session 2 months after the final experimental session. Subjects who do not live within reasonable driving distance of the study site (equal to or less than an estimated two hours' drive from the study site) must have a therapist in the area in which they live whom they can call on for support and evaluation if necessary;

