#### **6.1.1 Outcome Measures**

The primary outcome measure will be the CAPS, a clinician-scored measure for PTSD diagnosis and measure of symptom intensity and severity. The CAPS provides a means to evaluate the frequency and intensity dimensions of each symptom, impact of symptoms on the patient's social and occupational functioning, overall severity of the symptom complex and global improvement since baseline and the validity of the ratings obtained. The CAPS takes approximately one hour to complete. The CAPS interviews have been determined to have good internal consistency, concurrent validity, and test/retest reliability [78, 79]. An independent rater will assess all participants according to the Time and Events table.

The Global Assessment of Functioning (GAF) is a measure of global functioning and general function made through observations. The GAF consists of a single score, with scores ranging from 0 to 100, with 100 reflecting superior function and zero reflecting serious risk of causing harm to the self or others. The GAF will be recorded by the independent rater according to the Time and Events table.

The Beck Depression Inventory-II (BDI-II) is a 21-item a self-report measure of depressive symptoms [80] that will serve as a measure of depression. It takes five to ten minutes to complete. Participants will complete the BDI-II according to the Time and Events table.

The Post Traumatic Growth Inventory (PTGI) is a 21-item self-report measure of perceived growth or benefits occurring after a traumatic event. It contains five subscales; relationship to others, new possibilities, personal strength, spiritual change, and appreciation of life. In this study, participants will complete the PTGI in reference to the time since the trauma at baseline, but will respond in reference to the beginning of their participation in the study on all subsequent occasions. Participants will complete the PTGI according to the Time and Events table.

The DES-II is a 28-item self-report measure of dissociation, defined as a lack of normal integration of an individual's thoughts, feelings, or experiences into the stream of consciousness or memory [81, 82]. It is an established measure of dissociative symptoms. The scale consists of statements describing facets of dissociation. Respondents indicate how often the specific experience happens to them, from "never" to "always." Responses

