### 12.0 Data Analysis

The Sponsor will judge the clinical and statistical significance of the study and estimate effect size and statistical power based on a comparison of observer-blind data collected at baseline and the primary endpoint using the primary outcome measure, which is the CAPS.

The sample selection is expected to produce acceptably homogeneous groups due to their diagnosis of with PTSD with CAPS scores of at least 50 who have not responded to treatment. There is no expectation that conditions will differ significantly in composition by gender, race or ethnicity, duration of PTSD diagnosis or presence versus absence of other permitted psychiatric disorders, as depression.

The sponsor will examine individual CAPS, BDI-II, PTGI, PSQI, DES-II and GAF scores at baseline and the primary endpoint, in low dose, medium dose and full dose conditions. Descriptive statistics will be calculated for all measurements overall and by condition. Distributional characteristics will be examined for outliers and extreme values and, if either is evident. If outliers are found in primary or secondary outcome measures, the sponsor will perform analyses with and without the outlying data. Effect sizes for all outcome measures for primary endpoint, Stage 1, secondary endpoint, end of Stage 2, and 12-month follow-up will be estimated using Cohen's techniques.

All analyses of data from the primary endpoint will contain blinded data. Analysis of variance will be used to compare Global CAPS scores by dose condition at the primary endpoint.

Analysis of variance, or nonparametric analysis if assumptions are not met, will be used to compare the dose conditions for change in BDI-II, PTGI, PSQI, GAF, DES-II and NEO PI scores separately. If scores cannot be examined sufficiently in this model, then analyses will compare available data through the use of difference scores.

The sponsor will examine open-label data collected two months after the third Stage 1 experimental session. The sponsor will perform a within-subject analysis of full dose participants.

Subjects who discontinue treatment prior to the primary endpoint will be asked to complete an outcome assessment prior to continuing to the long-term follow-up. The data from these subjects will be tested for equivalence to data from subjects completing the study per protocol. If found to be equivalent, data from these subjects will be presented as

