### 12.1 Statistical power

The literature does not provide an estimate of the effect size for change in CAPS after sessions using an low dose or medium -dose MDMA. The proposed study will provide these important estimates. With the current amendment, the sponsor is increasing the group size in each condition, and all subjects will complete the primary endpoint. This may increase statistical power in this study, and will provide important estimates of effect size that can be used to develop a dose response model.

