## **8.9.2 Secondary Efficacy Analyses**

### **8.9.2.1 Secondary Efficacy Analyses at Primary Endpoint**

The secondary efficacy analyses will be made with ANOVA comparing change from baseline (visit 1) to the primary outcome timepoint (visit 13) of all the secondary measures. If the parametric assumptions for the ANOVA analyses are not met, the analogous nonparametric methods will be used (Kruskall-Wallis, Wilcoxon Rank-Sum).

Clinician Administered PTSD Scale-4 (CAPS-4) global scores will also be analyzed for effect size with the Cohen's *d* analysis.

Global Assessment of Functioning (GAF) total score will be analyzed in the same manner as the CAPS-4 global scale primary analysis.

Beck Depression Inventory-II (BDI-II) total score will be analyzed in the same manner as the CAPS-4 global scale primary analysis.

Post Traumatic Growth Inventory (PTGI) total will be analyzed in the same manner as the CAPS-4 global scale primary analysis.

Dissociative Experiences Scale-II (DES-II) total will be analyzed in the same manner as the CAPS-4 global scale primary analysis.

Pittsburgh Sleep Quality Index (PSQI) global scores will be analyzed in the same manner as the CAPS-4 global scale primary analysis.

NEO Personality Inventory (NEO PI) five factor scores will be analyzed in the same manner as the CAPS-4 global scale primary analysis.

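### The protocol leaves the primary CAPS variable ambiguous while the SAP tests change; align the two, preferably on a baseline-adjusted model

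*SAP*

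**What the plan says.** The SAP is explicit. Section 8.9.1 states "The primary efficacy evaluation is the change from baseline to the primary outcome timepoint (visit 13) in the CAPS-4 Global Severity score of PTSD", calls this a difference score, and tests it by ANOVA at alpha 0.05, with pairwise t-tests if the overall test rejects and rank tests if assumptions fail.

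The protocol can be read two ways.

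- Towards the endpoint score: the only CAPS test sentence in section 12.0 is "Analysis of variance will be used to compare Global CAPS scores by dose condition at the primary endpoint". The next paragraph names change for the secondary scales and then makes difference scores a fallback: "If scores cannot be examined sufficiently in this model, then analyses will compare available data through the use of difference scores".
- Towards change: the objective in section 3.1 is to "Assess changes in PTSD symptoms via Clinician-Administered PTSD Scale (CAPS) global scores"; section 12.0 opens with a comparison of baseline and primary-endpoint data; and section 12.1 says "The literature does not provide an estimate of the effect size for change in CAPS".

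Neither document mentions the difference in wording, and neither uses baseline CAPS as a covariate.

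On effect size, SAP 6.0 makes estimates for powering later studies a purpose of the trial. SAP 8.9.2.1 says only that CAPS "global scores will also be analyzed for effect size with the Cohen's" d. Protocol 12.0 likewise refers only to Cohen's techniques. Neither names the standardising SD, a small-sample correction or an interval.

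**The concern.** Two governing documents that support two different primary variables leave a choice open. Each subject is unblinded at Visit 13, and under SAP 8.10 the primary analysis waits until all subjects finish Stage 2. Every allocation is therefore known before the test is run. The choice should be closed in writing before then.

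Under randomisation, endpoint score, change score and ANCOVA all estimate the same mean dose difference, so this is not a question of bias. What differs is precision, and with 24 subjects that can decide the verdict. Which unadjusted analysis is more precise depends on two quantities that the documents do not give. Separately, a d whose denominator is not stated is hard to carry into a later sample-size calculation.

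**Working it through.** **Inputs from the documents.** Groups of 12 (full), 6 (medium) and 6 (low), two-sided alpha 0.05. There is no power calculation to reproduce: no SD, correlation, effect or power target is stated.

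**Assumptions.** Bivariate normal scores. Correlation r between baseline and Visit 13 from 0 to 0.7. Ratio k = endpoint SD / baseline SD of 1, 1.25 or 1.5. Values above 1 are included because entry requires subjects to "Have a CAPS score of 50 or higher, indicating moderate to severe PTSD symptoms", which may narrow the baseline spread. Shifts against low dose of 1.3 (full) and 0.65 (medium) endpoint SD, or 1.0 and 0.5.

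**Variance relative to the endpoint score.**

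- Change: 1 + 1/k² − 2r/k. It equals 1 when r = 1/(2k), that is r = 0.5 at k = 1 and r = 0.33 at k = 1.5.
- ANCOVA: (1 − r²)(1 + 1/(24 − 3 − 2)) = 1.053(1 − r²). The second factor is the expected cost of chance baseline imbalance.
- k = 1, r = 0.3: change 1 + 1 − 0.6 = 1.40; ANCOVA 1.053 × 0.91 = 0.96.
- k = 1, r = 0.7: change 1 + 1 − 1.4 = 0.60; ANCOVA 1.053 × 0.51 = 0.54.
- k = 1.5, r = 0.7: change 1 + 0.444 − 0.933 = 0.51; ANCOVA 0.54.

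**Power of the overall F test** (2 and 21 df for raw and change, 2 and 20 df for ANCOVA; 100,000 simulated trials per cell; shifts 1.3 and 0.65), as raw / change / ANCOVA in percent:

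| k | r = 0.3 | r = 0.5 | r = 0.7 |
|---|---|---|---|
| 1 | 59 / 44 / 60 | 59 / 59 / 70 | 59 / 82 / 86 |
| 1.25 | 59 / 52 / 60 | 59 / 66 / 69 | 59 / 87 / 86 |
| 1.5 | 59 / 56 / 60 | 59 / 70 / 70 | 59 / 88 / 86 |

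- ANCOVA minus change: +16 to +4 points at k = 1, +8 to −1 at 1.25, +4 to −2 at 1.5.
- Over all 36 scenarios (six values of r, three of k, two sets of shifts), the worst shortfall against the better of raw and change is 29 points for raw, 26 for change and 2.4 for ANCOVA.
- Raw and change reach different significance verdicts in 23 to 37% of trials (r 0.3 to 0.7, shifts 1.3 and 0.65), and in 6 to 9% under the null.
- Type I error is 4.9 to 5.1% for all three.
- The ANCOVA p-value for dose is the same whether the response is Visit 13 CAPS or change.

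**Effect size.** Take a true shift of 1.0 endpoint SD, r 0.3 to 0.7 and k 1 to 1.5.

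- By change SD, d = 1/√(1 + 1/k² − 2r/k): from 1/1.183 = 0.85 (k = 1, r = 0.3) to 1/0.715 = 1.40 (k = 1.5, r = 0.7).
- By baseline SD, d = k: 1.0 to 1.5.
- Small-sample factor J: 0.952 for 12 vs 6 and 0.923 for 6 vs 6, so uncorrected d runs about 5% and 8% high.
- 95% noncentral-t interval at d = 1.0: −0.05 to 2.02 (12 vs 6) and −0.23 to 2.19 (6 vs 6).

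**The case against.** The strongest reply is that the SAP already fixes the variable. It is the more specific document, its definitions section describes difference scores as the measure of change over time, and both documents state the objective as change. On that view one loose protocol sentence needs editing, and the 23 to 37% disagreement compares the SAP with an analysis it does not plan. This stands in part: the SAP alone gives a usable and valid test, and those figures argue for alignment rather than against the change score.

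Preferring ANCOVA to change could also be called taste. The trial sets no power target, the gain depends on assumed r and k, and it shrinks when k exceeds 1, the direction the entry cut-off suggests. That is fair about the size of the gain. But with r and k unknown, ANCOVA is the choice that does not need to guess them.

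A third point is conditional. If subjects have already passed Visit 13, changing the primary model would happen with allocations known. The documents do not show enrolment status when the SAP was written. Aligning the protocol sentence to the SAP avoids the problem.

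On effect size, SAP 8.9 reports n, mean and SD by group, so a reader could derive an interval. The plan does not commit to one, and it does not say which SD its own d will use.

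**Conclusion.** The concern holds. The protocol is ambiguous, not flatly contradictory, about the primary CAPS variable, and the two documents should be reconciled before the primary analysis. The SAP's change-score ANOVA controls error at 5%; its weakness is that its efficiency rests on an unknown correlation and SD ratio. Within the assumed ranges it can fall up to 26 points of power below raw scores, while raw scores can fall up to 29 below change. ANCOVA stays within 2.4 points of the better one throughout. These figures depend on normality and on assumed effects, correlations and SD ratios, none of which the documents supply. The undefined d is a secondary gap: the same true shift could be printed as anything from 0.85 to 1.5. This is a recommended change, not a fatal flaw.

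**What to change.** In SAP 8.9.1 and protocol 12.0, state one primary model: ANCOVA of Visit 13 CAPS on dose group with baseline CAPS as covariate. Take pairwise contrasts from that model, still only if the overall F test rejects, and name rank ANCOVA as the non-parametric fallback. Use the same model for GAF, BDI-II, PSQI, DES-II and NEO PI. Leave PTGI out and say why: at baseline subjects answer about the time since the trauma, "but will respond in reference to the beginning of their participation in the study on all subsequent occasions", so its baseline is not a like-for-like covariate. Report the adjusted mean difference and Hedges' g with 95% intervals, and name the SD used for g.

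If the sponsor keeps change scores, or if Visit 13 results are already known by arm, the minimum is to make the CAPS sentence in protocol 12.0 say change and to define d.

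The cost is wording; no new data are needed. ANCOVA uses one residual degree of freedom (21 to 20) and assumes a common slope, which six subjects per arm can hardly check. It gives up at most 2.4 points of power against raw scores when r is 0.2 or less, and about 1 to 2 points against change scores when endpoint spread is well above baseline spread and r is 0.5 to 0.7.
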